### 10.3.2 Safety Analyses

All safety analyses will be performed on the treated population.

**Table 10.3.2-1: Safety - Statistical Analyses**

Endpoint	Statistical Analysis Methods
Incidence of DLTs, AEs, SAEs, AEs leading to discontinuation, and death.  AEs will be graded according to CTCAE v4.03.	DLT rate by dose level, frequency distribution of treated participants with AE using the worst CTC grade. Participants will only be counted (1) once at the PT level, (2) once at the system organ class level, and (3) once in the 'total participant' row at their worst CTC grade, regardless of system organ class or PT.
Toxicity Changes from Baseline.  Laboratory values will be graded according to CTCAE v4.03.	Laboratory shift table using the worst CTC grade on-treatment per participant.

Abbreviations: CTC = common terminology criteria; PT = preferred term.

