**Table 4-1: Objectives and Endpoints**

Objectives	Endpoints

Primary
 

• To characterize the safety, tolerability, and DLTs and to determine the MTD/RP2D of BMS-986218 administered as monotherapy and in combination with nivolumab in participants with advanced solid tumors

• To evaluate the efficacy and safety of BMS-986218 monotherapy relative to ipilimumab in participants with advanced cutaneous melanoma previously treated with anti-PD-1/PD-L1 immunotherapy (Part 2A only)

• To evaluate the efficacy and safety of BMS-986218 alone and in combination with nivolumab in NSCLC (Part 2B and Part 2C)

	

• Incidence of AEs, SAEs, AEs meeting protocol-defined DLT criteria, AEs leading to discontinuation, and death

• ORR, mDOR, and PFSR at 24, 36, and 48 weeks by RECIST v1.1

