#### **5.1.2.4 The Randomized BMS-986218 Monotherapy Cohort Expansion in Cutaneous Melanoma (Part 2A), the BMS-986218 Cohort Expansion - Monotherapy (Part 2B), and the BMS-986218 Cohort Expansion - Combination Therapy (Part 2C and Part 2D)**

The purpose of the BMS-986218 cohort expansions is to gather preliminary efficacy information in specific patient populations regarding BMS-986218 alone and in combination with nivolumab.

Continuous evaluation of toxicity events in the BMS-986218 cohort expansions will be performed throughout enrollment for all expansion cohorts. If, at any time, the aggregate rate of treatment-related toxicities meeting DLT criteria exceeds 33% across all participants treated in cohort expansions, the findings will be discussed, and further enrollment will be interrupted. Depending on the nature and grade of the toxicity, and after assessing the benefit-risk ratio, a new dose for all cohorts may be initiated at a previously tested lower dose level or at a dose level intermediate to previously tested lower dose levels.

The Randomized BMS-986218 Monotherapy Cohort Expansion in Cutaneous Melanoma (Part 2A) will evaluate the preliminary efficacy of BMS-986218 monotherapy relative to ipilimumab monotherapy in a cohort of participants with advanced cutaneous melanoma who have received prior immunotherapy with an anti-PD-1 or anti-PD-L1 containing regimen and must have progressive or recurrent disease after prior anti-PD-1/PD-L1 directed therapy. Participants must not have received prior anti-CTLA-4 therapy. Three dose levels or schedules for BMS-986218 from the Part 1A Q4W monotherapy escalation will be evaluated that have had at least 6 DLT evaluable participants and meet safety criteria: one at 7 mg Q4W, one at 20 mg Q4W, and one at 70 mg Q4W, and ipilimumab 3 mg/kg (Q3W, 3-week treatment cycle for up to a maximum of 4 doses [which are to be completed within 16 weeks of the first dose in case of any delays]).

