### 7.4 Method of Treatment Assignment

During the screening visit, the investigative site will call into the enrollment option of the IRT designated by BMS for assignment of a 5-digit participant number that will be unique across all sites. Enrolled participants, including those not dosed, will be assigned sequential participant numbers [REDACTED]. The patient identification number

(PID) will ultimately be comprised of the site number and participant number. For example, the first participant screened (ie, enrolled) at site number 1, will have a PID of [REDACTED]. Once it is determined that the participant meets the eligibility criteria following the screening visit, the investigative site will call the IRT to centrally assign the participant into the open dose panel. If Part 1 is open upon the decision to initiate Part 2, treatment in the 2 parts will occur in parallel.

In the Randomized BMS-986218 Monotherapy Cohort Expansion in Cutaneous Melanoma (Part 2A), all participants will be centrally randomized evenly across study arms, which will include: BMS-986218 monotherapy at 7 mg, 20 mg, 70 mg Q4W or ipilimumab 3 mg/kg Q3W (maximum of 4 doses).

In the Randomized BMS-986218 Monotherapy Cohort Expansion (Part 2B), participants will be randomized evenly across study arms, which will include: BMS-986218 at 7 mg, 20 mg, and 70 mg Q4W.

In Part 2A and Part 2B, if it is decided based on a preliminary assessment of anti-tumor activity that not all arms would need to continue enrollment, randomization would continue only in the arm(s) that remain open. In addition, more subjects may be enrolled in selected arm(s) as specified in [Section 5.2](#) to better assess an initial signal.

In Part 2C Combination Expansion, multiple doses may be open concurrently. In that case, treatment assignments will alternate between the dose levels, with consecutively treated participants assigned to different parts through IRT whenever possible. If there are no openings available in the dose level to which the participant would be assigned by this algorithm, then the subject will be assigned to the next open dose.

In Part 2D Combination Expansion, participants will be assigned to one dose.

In Part 2, BMS-986218 Q4W will be administered for a maximum duration of 2 calendar years, and ipilimumab Q3W will be administered for a maximum of 4 doses.

For Part 2, participant replacement will not be allowed for participants who are discontinued after dosing.

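### Part 2A plans only crude AE percentages over unequal observation windows; add cumulative incidence at a common time from first dose

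*Combined protocol and SAP*

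**What the plan says.** Table 4-1 gives as a primary objective for Part 2A: "To evaluate the efficacy and safety of BMS-986218 monotherapy relative to ipilimumab in participants with advanced cutaneous melanoma". The matching safety endpoint is "Incidence of AEs, SAEs, AEs meeting protocol-defined DLT criteria, AEs leading to discontinuation, and death", with no time base. Section 5.4.3 names safety among the things that the head-to-head comparison is meant to show.

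The method is in Section 10.3.2: "All safety analyses will be performed on the treated population". Table 10.3.2-1 then lists the DLT rate by dose level, the "frequency distribution of treated participants with AE using the worst CTC grade" (each participant counted once at each level), and a laboratory shift table. It gives no person-time rate, time-to-event summary or common window. For efficacy in the same objective, Table 10.3.1-1 does fix common times: Kaplan-Meier PFS rates at 24, 36 and 48 weeks, with a difference from ipilimumab.

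Treatment length differs by design. Section 7.4 says that "BMS-986218 Q4W will be administered for a maximum duration of 2 calendar years" and that "ipilimumab Q3W will be administered for a maximum of 4 doses". Section 5.1.2.4 adds, of the four ipilimumab doses, "which are to be completed within 16 weeks of the first dose in case of any delays". Tables 2-2 and 2-4 and Section 5.1.3.1 carry AE collection to 100 days after the last dose in every arm.

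**The concern.** A percentage of participants with at least one event rises with the time over which events are counted. Here that time is set by each arm's dosing rule and by how long each participant stays on treatment. If BMS-986218 and ipilimumab carried the same risk per week, the arm treated longer could still show the higher percentage. The relative-safety objective would then be read from a table that cannot separate a more toxic drug from a drug given for longer. AEs leading to discontinuation are more exposed than AEs in general, because they can arise only while dosing continues: about 9 to 16 weeks on ipilimumab against up to 104 on BMS-986218. The worst on-treatment laboratory grade has the same feature.

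**Working it through.** The plan states no AE window in weeks and no AE rate for Part 2A, so there is no figure of its own to reproduce on this point.

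**Windows** (last dose + 100/7 = 14.3 weeks):
- Ipilimumab, doses at weeks 0, 3, 6 and 9: 9 + 14.3 = 23.3 weeks.
- Ipilimumab with the delays in Section 5.1.2.4: 16 + 14.3 = 30.3 weeks.
- BMS-986218, maximum: 104 + 14.3 = 118.3 weeks.
- Ratio at the maximum: 118.3/23.3 = 5.1, or 118.3/30.3 = 3.9 against delayed ipilimumab.
- A participant who stops at the week-12 scan: 8 + 14.3 = 22.3 weeks on BMS-986218 against 23.3 on ipilimumab, nearly equal.

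**Constant equal hazard.** Assumptions, none from the documents: 30% incidence over 23.3 weeks in both arms, so λ = −ln(0.70)/23.3 = 0.0153 per week; exponential time to stopping with median m, the same in both arms, r = ln 2/m; no delays. With dosing interval s, the probability that the last dose falls at week s·k is exp(−r·s·k) − exp(−r·s·(k+1)), and all remaining probability sits at the cap (week 9 or week 104). Crude incidence is the sum of these probabilities times 1 − exp[−λ(s·k + 14.3)].

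Example, ipilimumab at m = 12: probabilities 0.159, 0.134, 0.113 and 0.595 times 19.7, 23.3, 26.7 and 30.0% give 27.1%.

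| Median weeks on treatment | Mean window, BMS-986218 / ipilimumab (weeks) | Crude incidence, BMS-986218 | Crude incidence, ipilimumab | Gap (points) |
|---|---|---|---|---|
| 6 | 21.1 / 19.0 | 27.0% | 25.1% | 1.9 |
| 8 | 23.9 / 19.8 | 29.7% | 26.0% | 3.7 |
| 12 | 29.6 / 20.7 | 34.6% | 27.1% | 7.5 |
| 16 | 35.1 / 21.3 | 38.8% | 27.7% | 11.1 |
| 24 | 45.3 / 21.9 | 45.6% | 28.4% | 17.2 |

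The share still on treatment at two years is exp(−104r): 0.2% at m = 12 and 5.0% at m = 24.

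With a lower base rate of 18% (Appendix 11, Table 1: treatment-related Grade 3-4 AEs, ipilimumab 3 mg/kg), the same model gives 21.5% against 16.1% at m = 12 and 30.1% against 17.0% at m = 24.

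**Early risk only.** If all risk falls in the first 12 weeks, the gap is 0, because even a single dose gives a 14.3-week window. If the hazard stops at week 24, the gap stays within half a point for every m above.

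**Person-time rates as an alternative.** With 30% incidence and all risk in the first 12 weeks, crude incidence is about 30% in both arms. Events per 100 person-years (time to first event or end of window) become about 70 against 96 at m = 12 and about 47 against 92 at m = 24. The bias then runs in favour of BMS-986218.

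**The case against.** Crude incidence over the regimen as given answers a legitimate question: how many participants each regimen harms. Section 5.4.3 describes recurrent immune stimulation as something to be evaluated, so toxicity from longer dosing is partly the effect of interest. This stands, and it is why the crude table should remain.

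Table 10.3.2-1 defines no between-arm safety difference, and Section 3.2.1 says that no prospective hypotheses are formally evaluated. With 33 per arm and 30% incidence, the 95% half-width for a difference is 1.96 × √(2 × 0.3 × 0.7/33) = 22 points, wider than the largest gap shown. These facts lower the stakes. They do not remove the problem, because a descriptive table is still what the relative-safety objective will be read from, and a systematic gap is not sampling noise.

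Section 10.3 calls its content a summary, with a SAP to be finalized before database lock. That SAP could add what is missing, but the protocol does not say that it will.

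A reader might infer that the comparison is 23 weeks against 118, or that the safety question cannot be answered at all. The documents support neither. The 118 weeks is a maximum, permitted delays take ipilimumab to about 30 weeks, and Section 9.2.1 can end collection of non-serious AEs earlier, at new anti-neoplastic treatment. The data for a fair summary are already collected. Deaths need not be affected, because survival follow-up runs to 4 years from first dose in all arms.

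**Conclusion.** The point holds as a gap in the planned safety summary for Part 2A. The AE windows differ by design, the planned percentages take no account of this, and any resulting bias under equal hazard mainly runs against BMS-986218. Its size is not established: about 0 points if risk is confined to the first 12 to 24 weeks, and about 2 to 17 points under a constant hazard with median treatment of 6 to 24 weeks. The documents give neither the time course of AE risk nor the expected time on treatment, and crude percentages cannot show which case applies.

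**What to change.** Keep the crude table, labelled as the summary of each regimen as given. For Part 2A, add to Table 10.3.2-1 the cumulative incidence by arm, from first dose, of (a) first Grade 3+ treatment-related AE and (b) first AE leading to discontinuation. Treat death as a competing event, and censor at the end of the AE collection window.

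Choose a time inside both windows. Twelve weeks suits both outputs: a single dose already gives 14.3 weeks of collection, and an undelayed ipilimumab participant has had the last planned dose by week 9. About 20 weeks is the outer limit; it already relies on censoring, since an ipilimumab participant needs three doses to reach it (6 + 14.3 = 20.3). At 24 weeks the ipilimumab estimate would rest only on participants with delayed doses, who may have been delayed because of toxicity.

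State when AE collection ends. Section 9.2.1 stops collection of non-serious AEs at new anti-neoplastic treatment in one place and asks for at least 100 days in another; the censoring rule needs a single reading.

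Exposure-adjusted rates may be shown as supportive, with a note that they assume a constant hazard and can favour the longer-treated arm if AEs occur early.

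Cost: one or two extra outputs, with no new data and no change in sample size.

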**10.3.3 Pharmacokinetic Analysis for BMS-986218****Table 10.3.3-1: Pharmacokinetic - Statistical Analyses**

Endpoint	Statistical Analysis Methods
Cmax, AUC(0-T), AUC(TAU), Ctau, CLT, Css-avg, AI_Cmax, AI_AUC, and T-HALF	Summary statistics: geometric means and coefficients of variation
Cmax, AUC(0-T), AUC(TAU)	Scatter plots vs dose for each cycle measured; dose proportionality based on a power model and a CI around the power coefficient
Tmax	Summary statistics: medians and ranges
Ctrough	Summary statistics to assess attainment of steady state: geometric means and coefficients of variation, by treatment and by day; plots vs time by dose

Abbreviations: AI\_AUC = ratio of an exposure measure at steady state to that after the first dose (exposure measure includes AUC[TAU]); AI\_Cmax = ratio of an exposure measure at steady state to that after the first dose (exposure measure includes Cmax); AUC(0-T) = area under the plasma serum concentration-time curve from time zero to time of last quantifiable concentration (may be calculated if concentrations are not quantifiable up to TAU across a treatment group); AUC(TAU) = area under the serum concentration-time curve in 1 dosing interval; CLT = total body clearance; Css-avg = average serum concentration over a dosing interval (AUC[TAU]/tau) at steady state; Ctau = observed serum concentration at the end of a dosing interval; Ctrough = trough observed serum concentrations (this includes predose concentrations [C0] and Ctau); T-HALF = terminal serum half-life; Tmax = time of maximum observed plasma serum concentration.

PK serum concentration-time data for BMS-986218, ipilimumab, and/or nivolumab may be pooled with data from other studies for integrated population PK and ER analyses, which will be presented in a separate report.

**10.3.4 Immunogenicity**

Endpoint	Statistical Analysis Methods
Incidence of ADA  Baseline ADA-positive participant is defined as a participant who has an ADA-detected sample at baseline a,b ADA positive- participant is a participant with at least 1 ADA-positive sample relative to baseline after initiation of the treatment	Frequency distribution of baseline ADA-positive participants and ADA-positive participants after initiation of the treatment

a Baseline sample is the last sample before initiation of the treatment.

b Details of the immunogenicity data analysis, including ADA titers, will be provided in the Statistical Analysis Plan.

#### **10.3.9 *Interim Analyses***

Interim analyses will be performed for administrative purposes, internal decisions, or publications and they will be descriptive. No formal inferences requiring any adjustment to statistical significance level will be performed.

Preliminary efficacy may be assessed for Part 2 to determine an initial signal, and enrollment may be paused, prior to enrolling additional participants. Depending on enrollment rate and preliminary data there may not be a pause in enrollment. If an inadequate signal is detected from a preliminary analysis, then enrollment may be closed for that cohort.

## 12. APPENDICES

**APPENDIX 1 ABBREVIATIONS AND TRADEMARKS**

Term	Definition
Ab	antibody
ADA	anti-drug antibody
ADCC	antibody-dependent cellular cytotoxicity
AE	adverse event
AI	accumulation index
AI_AUC	accumulation index ratio of AUC at steady state to that after the first dose
ALK	anaplastic lymphoma kinase
ALP	alkaline phosphatase
ALT	alanine aminotransferase
AST	aspartate aminotransferase
AUC	area under the concentration-time curve
AUC(0-xh)	area under the concentration-time curve from time zero to x hours
AUC(0-T)	area under the concentration-time curve from time zero to the time of the last quantifiable concentration
AUC(TAU)	area under the concentration-time curve in 1 dosing interval
Avg	average
BLRM	Bayesian Logistic Regression Model
BMS	Bristol-Myers Squibb
BOR	best overall response
BRAF	v-raf murine sarcoma viral oncogene homolog B1
BUN	blood urea nitrogen
C	cycle
Cavg	average concentration
Cavgss	average steady state concentration
CD	cluster differentiation
cHL	classical Hodgkin Lymphoma
CI	confidence interval
CL	clearance
CLT	total body clearance

Term	Definition
CLTp	total plasma clearance
Cmax	maximum observed plasma concentration
CNS	central nervous system
COVID-19	Coronavirus Disease 2019
CR	complete response
CRC	colorectal cancer
CrCl	creatinine clearance
CRF	case report form
Css-avg	average concentration over a dosing interval (AUC[TAU]/tau) at steady state
CT	computed tomography
CTAg	Clinical Trial Agreement
Ctau	observed concentration at the end of a dosing interval
CTC	common terminology criteria
CTCAE	Common Terminology Criteria for Adverse Events
CTLA-4	cytotoxic T-lymphocyte-associated protein 4
Ctrough	trough observed plasma concentration
D	day
DLT	dose-limiting toxicity
DNA	deoxyribonucleic acid
DOR	duration of response
EAU 50	area-under-the-concentration-time curve producing 50% of the maximum effect
EC50	concentration required for 50% efficacy
ECG	electrocardiogram
ECOG	Eastern Cooperative Oncology Group
eCRF	electronic Case Report Form
EGFR	epidermal growth factor receptor
EMAX	maximum effect
EOI	end of infusion

Term	Definition
EOT	end of treatment
ER	exposure response
EWOC	escalation with overdose control
FcR	Fc receptor
FDA	Food and Drug Administration
FDG	2-deoxy-2-[  F]fluoro-D-glucose
FIH	first-in-human
FNR	false negative rate
FPR	false positive rate
FSH	Follicle stimulating hormone
GI	gastrointestinal
GE	gastroesophageal
GnRH	gonadotropin-releasing hormone
HCC	hepatocellular carcinoma
hCG	human chorionic gonadotropin
hIgG1	human immunoglobulin G1
HIV	human immunodeficiency virus
HNSTD	highest non-severely toxic dose
IB	Investigator Brochure
ICF	informed consent form
IFN- $\gamma$	interferon gamma
Ig	immunoglobulin
IL	interleukin

Term	Definition
IMP	investigational medicinal product
IND	Investigational New Drug
I-O	immuno-oncology
IP	investigational product
IPRES	Innate PD-1 RESistance
irAE	immune-related adverse event
IRR	infusion-related reaction
IRT	Interactive Response Technology
IV	intravenous
Kd	constant of dissociation
KRAS	Kirsten rat sarcoma viral oncogene homolog
LHRH	luteinizing hormone releasing hormone
mAb	monoclonal antibody
MAP	meta-analytic predictive
mCRPC	metastatic castration-resistant prostate cancer
mDOR	median duration of response
[REDACTED]	[REDACTED]
[REDACTED]	[REDACTED]
MRI	magnetic resonance imaging
MSS	microsatellite stable
[REDACTED]	[REDACTED]
MTD	maximum tolerated dose
NF	non-fucosylated
NK	natural killer (cell)
NRAS	neuroblastoma rat viral oncogene homolog
NSCLC	non-small cell lung cancer
ORR	objective response rate
OS	overall survival
OSR	overall survival rate
PBMC	peripheral blood mononuclear cell
PCR	polymerase chain reaction

Term	Definition
PCWG 3	Prostate Cancer Working Group 3
PD	pharmacodynamic
PD-1	programmed cell death 1
PDAC	pancreatic ductal adenocarcinoma
PD-L1	programmed death ligand 1
PD-L2	programmed death ligand 2
p-DILI	potential drug-induced liver injury
PE	physical examination
PET	positron emission tomography
PrEE	probability of early efficacy
PrET	probability of early termination
PFS	progression-free survival
PFSR	progression-free survival rate
PI	prediction interval
PID	patient identification number
PK	pharmacokinetic/s
PPK	population pharmacokinetics
PR	partial response
[REDACTED]	[REDACTED]
PT	preferred term
Q2W	every 2 weeks
Q3W	every 3 weeks
Q4W	every 4 weeks
Q8W	every 8 weeks
Q12W	every 12 weeks
[REDACTED]	[REDACTED]
[REDACTED]	[REDACTED]
QTcF	QT interval corrected for heart rate using Fridericia's formula
RAS	rat sarcoma
RCC	renal cell carcinoma

Term	Definition
RECIST	Response Evaluation Criteria in Solid Tumors
RNA	ribonucleic acid
[REDACTED]	[REDACTED]
RP2D	recommended Phase 2 dose
RP2D-1	1 dose level below the recommended Phase 2 dose of BMS 986218
RT-PCR	reverse transcription polymerase chain reaction
SAE	serious adverse event
SARS-CoV-2	severe acute respiratory syndrome coronavirus 2
[REDACTED]	[REDACTED]
SCC	squamous cell carcinoma
SCCHN	squamous cell carcinoma of the head and neck
SD	stable disease
SMT	Safety Management Team
[REDACTED]	[REDACTED]
SPR	surface plasmon resonance
T3	triiodothyronine
T4	thyroxine
[REDACTED]	[REDACTED]
TGI	tumor growth inhibition
T-HALF	terminal serum half-life
Tmax	time of maximum observed concentration
TNBC	triple-negative breast cancer
TNF- $\alpha$	tumor necrosis factor alpha
Treg	T-regulatory cell
TSH	thyroid stimulating hormone
ULN	upper limit of normal
US	United States
[REDACTED]	[REDACTED]
Vss	steady-state volume of distribution
WOCBP	women of childbearing potential

Term	Definition
WWPS	Worldwide Patient Safety

## **APPENDIX 2        STUDY GOVERNANCE CONSIDERATIONS**

The term 'Participant' is used in the protocol to refer to a person who has consented to participate in the clinical research study. The term 'Subject' used in the CRF is intended to refer to a person (Participant) who has consented to participate in the clinical research study.

### **REGULATORY AND ETHICAL CONSIDERATIONS**

#### **GOOD CLINICAL PRACTICE**

This study will be conducted in accordance with:

- Consensus ethical principles derived from international guidelines including the Declaration of Helsinki and Council for International Organizations of Medical Sciences (CIOMS) International Ethical Guidelines Good Clinical Practice (GCP).
- as defined by the International Council on Harmonisation (ICH).
- in accordance with the ethical principles underlying European Union Directive 2001/20/EC.
- United States Code of Federal Regulations, Title 21, Part 50 (21CFR50).
- applicable local requirements.

The study will be conducted in compliance with the protocol. The protocol and any amendments and the participant informed consent will receive approval/favorable opinion by Institutional Review Board/Independent Ethics Committee (IRB/IEC), and regulatory authorities according to applicable local regulations prior to initiation of the study.

All potential serious breaches must be reported to the Sponsor or designee immediately. A potential serious breach is defined as a Quality Issue (eg, protocol deviation, etc) that is likely to affect, to a significant degree, one or more of the following: (1) the physical safety or mental integrity of one or more subjects/participants; (2) the scientific value of the trial (eg, reliability and robustness of generated data). Items (1) or (2) can be associated with either GCP Regulation(s) or Trial protocol(s).

Personnel involved in conducting this study will be qualified by education, training, and experience to perform their respective tasks.

This study will not use the services of study personnel where sanctions have been invoked or where there has been scientific misconduct or fraud (eg, loss of medical licensure, debarment).

